## 1. VERSION HISTORY

**Table 1. Summary of Major Changes in SAP Amendments**

Version/ Date	Associated Protocol Amendment	Rationale	Specific Changes
1.0 05 Aug 2020	Original 8 May 2020	Not Applicable	Not Applicable
2.0 28 Sep 2021	Amendment 1 20 Apr 2021	To match TLF	Add abbreviations to the analysis set
		For clarification	In section 5.2, elaborate the “Binary safety data”
		To assess the impact of COVID-19	In section 6.7, add COVID-19 related safety analysis
		For clarification	Add appendix 2, list of countries for regions
		For clarification	Add details to calculate cumulative dose/compliance by visit in Section 6.6.3 and appendix 3
		ECG analysis was missing in version 1	Add ECG analysis in Section 6.2.9
		For clarification	Added details to calculate cumulative dose and compliance in appendix 3.
		For clarification	In section 7, specified only data up to Month 9 will be included in the analysis for PCD
3.0 22 Nov 2021	Amendment 1 20 Apr 2021	For clarification	In section 7, update the scope of PCD CSR, and unblinding/blinding status of sponsors, investigators and participants after PCD
		For clarification	In section 3.6.3, specified that only QTcF interval will be analyzed, instead of all ECG parameters
		Team decision	Delete the analysis of physical examinations, C-SSRS, and cumulative dose up to each visit
4.0 17 Aug 2022	Amendment 2 28 Apr 2022	Updated to incorporate changes in protocol amendment 2	In section 2, updated the study objects and endpoints, study design

**Table 1. Summary of Major Changes in SAP Amendments**

Version/ Date	Associated Protocol Amendment	Rationale	Specific Changes
		Updated to incorporate changes in protocol amendment 2	Added exploratory efficacy endpoints in section 3.4
		Clarify according to PCD CSR	Add clarification in section 3.2 “For each participant, data were reported as the percentage of IENF with any number of swellings. The endpoint “axonal dystrophy” refers to the percentage of IENF with axonal swellings.”, similar in section 6.2.2 ”
		This analysis was added to the PCD CSR to assist with the interpretation of secondary endpoints	In section 6.2.3, the following analysis was added, “Descriptive Summary of absolute and change from baseline in IENFD normalized by age and gender.”
		This analysis was added to the PCD CSR to assist with the interpretation of the secondary endpoints	In section 6.2.4 “percent change from baseline in amplitude of wave V on BAEP at a stimulus intensity of 80dB at Months 6, 9, 9E, and 15E” was added
		Updated to incorporate changes in protocol amendment 2	Section 8 and Section 9 were added to specify the timing of each analysis and the endpoints included in each CSR.
		Updated to incorporate changes in protocol amendment 2	Section 11, the analysis visit window definition was updated to include TP3
5.0 04 April 2023	Amendment 2 28 Apr 2022	Update to include the definition of risk period for the purpose of summarizing	Section 3.6.1, add the definitions of risk periods for the summaries of AEs.

**Table 1. Summary of Major Changes in SAP Amendments**

Version/ Date	Associated Protocol Amendment	Rationale	Specific Changes
		safety data. This update was made for consistency with the AA ritlecitinib program.	
		clarified that the Overall column in binary summary tables will also include the observation period	Section 8.2, Added table 4.
		Clarification of the statistical method used to analyze continuous endpoints	Section 5.2. General methods. Remove ‘and subject as a random effect’, and add instructions on how to run the model in SAS in case of convergence issues.
		Clarification that the linear mixed-effects model includes not only the primary timepoint, but also other timepoints	In Sections 6.1. and 6.2.1. added added ‘which includes all post-baseline measurements through ...’ to the statistical methods.
		Clarification of the statistical method used for the overall and AA SALT scores	Section 6.3.1. Removed the details describing the linear mixed-effects model,

## 2. INTRODUCTION

This SAP provides the detailed methodology for summary and statistical analyses of the data collected in study B7981037. This document may modify the plans outlined in the protocol; however, any major modifications of the primary endpoint definition or its analysis will also be reflected in a protocol amendment.

### 2.1. Study Objectives, Endpoints, and Estimands

The study objectives and corresponding endpoints are listed below in [Table 2](#). Estimands are not applicable since there is no formal statistical hypothesis testing for this study.

**Table 2. Study Objectives and Endpoints**

Objectives	Endpoints
Primary – Safety	

 
To assess I-V interwave latency on brainstem auditory evoked potentials (BAEPs) in adult participants with alopecia areata (AA) treated with PF-06651600.
 
	
 
Change from baseline in I-V interwave latency on BAEP at a stimulus intensity of 80 decibels (dB) at Month 9.
 

Secondary – Safety	

 
To assess I-V interwave latency on BAEPs in adult participants with AA treated with PF-06651600.
 
	
 
Change from baseline in I-V interwave latency on BAEP at a stimulus intensity of 80dB at Months 6, 9E, and 15E.
 

 
To assess axonal dystrophy in intraepidermal nerve endings over time in adult participants with AA treated with PF-06651600.
 
	
 
Change from baseline in axonal dystrophy in skin punch biopsies at Month 9 and Month 15E.
 

 
To assess intraepidermal nerve fiber density (IENFD) over time in adult participants with AA treated with PF06651600.
 
	
 
Change from baseline in IENFD in skin punch biopsies at Month 9 and Month 15E.
 

 
To assess wave V amplitude on BAEP over time in adult participants with AA treated with PF-06651600.
 
	
 
Change from baseline in amplitude of wave V on BAEP at a stimulus intensity of 80dB at Months 6, 9, 9E, and 15E.
 

 
To assess presence of wave V on BAEP over time in adult participants with AA treated with PF-06651600.
 
	
 
Absence of wave V on BAEP at stimulus intensities ranging from 80dB to 40dB at Months 6, 9, 9E, and 15E.
 

 
To evaluate the safety and tolerability of PF-06651600 in adult participants with AA.
 
	
 
Incidence of treatment emergent adverse events (TEAEs), treatment-emergent serious adverse events (TESAEs), and adverse events (AEs) leading to discontinuation;a
 
Incidence of clinically significant abnormalities in vital signs and ECG;a
 

**Table 2. Study Objectives and Endpoints**

Objectives	Endpoints
	
 
Incidence of clinically significant abnormalities in clinical laboratory values.a
 

Secondary – Efficacy TP1-TP2	

 
To evaluate response to PF-06651600 measured by the Severity of Alopecia Tool (SALT) in adult participants with AA.
 
	
 
Change from baseline in overall and AA SALT score at Month 9 and other time points collected.a
 

 
To evaluate the response to PF-06651600 measured by the Patient’s Global Impression of Change (PGI-C) tool in adult participants with AA.
 
	
 
PGI-C score response defined as greatly improved or moderately improved from baseline at Month 9 and other time points collected.
 

Tertiary/Exploratory-Efficacy TP3	

 
To evaluate long-term response to PF 06651600 measured by the Severity of Alopecia Tool (SALT) in adult participants with AA.
 
	
 
Change from baseline in overall and AA SALTb score at Month 51E and other time points collected.
 

 
To evaluate the long-term response to PF-06651600 measured by the Patient’s Global Impression of Change (PGI-C) tool in adult participants with AA.
 
	
 
PGI-C score response defined as greatly improved or moderately improved at Month 51E and other time points collected.
 

a. Refer to [Section 9](#) for specific safety summary included in each clinical study report

b. AA SALT is the amount of scalp hair loss due to AA.

## 2.2. Study Design

This is a Phase 2a, randomized, double-blind, placebo-controlled safety study designed to evaluate the safety and tolerability of PF-06651600, including the assessments of BAEP and IENF, in adults 18 to ≤50 years of age with ≥25% scalp hair loss due to AA.

### **Treatment Period 1 (TP1) and Treatment Period 2 (TP2):**

The total duration of participation in the study for TP1 and TP2 will be approximately 26 months.

This includes up to a 5-week screening period, a 9-month placebo-controlled treatment phase, a 15-month active therapy extension phase, and a 4-week follow-up

period [for participants not continuing to TP3 or discontinuation of study intervention]. Screening will occur within 35 days prior to Day 1 of the study to confirm that selection criteria for the study are met. At Month 9, the placebo-controlled phase will end, and all participants may enter the active therapy extension phase of the study and receive PF- 06651600. For any participant discontinued for a neurological or auditory adverse event, the participant will be evaluated again at 6 months after discontinuation; the maximum duration of participation in the study for such participants could be approximately 32 months if the event occurred at the last visit.

### **Treatment Period 3 (TP3):**

The total duration for TP3 will be of variable length for individual participants; assuming a participant does not require discontinuation per protocol. A participant may continue to receive PF-06651600 in TP3 for a maximum of an additional 36 months or until availability of commercial product in their country, or until the Sponsor terminates the study in that country, whichever occurs first.

[figure not shown]
In TP3, participants will receive 50 mg QD PF-06651600. The total duration of participation in TP3 is approximately 37 months, including up to 36 months study intervention, and a follow up period of 4 weeks after completion or discontinuation of study intervention.

### **Observation Period:**

If study intervention is permanently discontinued, the participant will be asked to remain in the study after the Follow-up visit without study intervention, and continue to comply with study visit schedules for approximately 2 years after the last dose of study intervention or until study end, whichever occurs first.

A study design schematic is presented in [Figure 1](#).

**Figure 1. Study Design Schematic**

Abbreviations; E= active therapy extension phase; QD = once daily; TP = Treatment Period

- a. Any participant with baseline overall SALT score  $\leq 75$  will be given the option to enter the active therapy extension phase at Month 6 if the overall SALT score at Month 6 has increased from baseline by  $\geq 25$  points.
- b. After completion of TP2 (for participants not continuing to TP3) or discontinuation of study intervention, a Follow-up period of 4 weeks will occur. Participants in countries where PF-06651600 is not commercially available at the time their Month 24 visit will have the opportunity to enter TP3, of variable length for individual participants for a maximum of 36 months or until availability of commercial product in their country, or until the Sponsor terminates the study in that country, whichever occurs first
- c. In TP3, after completion or discontinuation of study intervention, a Follow-up period of 4 weeks will occur.
- d. If study intervention is permanently discontinued, the participant will be asked to remain in the study after the Follow-up visit for the Observation Period without study intervention and continue to comply with study visit schedules for approximately 2 years or until study end, whichever occurs first.

Note: If a participant discontinues for neurological or audiological events at any time during the study, a follow-up period of 6 months will occur.

## Sample Size Determination

Approximately 60 adults 18 to 50 years of age will be randomized in a 1:1 allocation ratio to either the PF-06651600 200 mg QD/50 mg QD dose group or the placebo group.

For the primary safety endpoint, change from baseline in I-V interwave latency on BAEP at Month 9, the published standard deviations for I-V interwave latency on BAEP range from 0.1 to 0.3 ms. Assuming a standard deviation of 0.2 ms, and assuming the standard deviation of change from baseline is similar to the standard deviation of actual score, the half-width of 95% confidence interval for the group will be 0.07 ms for 30 participants per group.

## 3. ENDPOINTS AND BASELINE VARIABLES: DEFINITIONS AND CONVENTIONS

### 3.1. Primary Endpoint – Safety in TP1

- Change from baseline in I-V interwave latency on BAEP at a stimulus intensity of 80 decibels (dB) at Month 9.

### 3.2. Secondary Endpoints – Safety in TP1+TP2

- Change from baseline in I-V interwave latency on BAEP at a stimulus intensity of 80dB at Months 6, 9E, and 15E;
- Change from baseline in axonal dystrophy in skin punch biopsies at Month 9 and Month 15E;
  - For each participant, data was reported as the percentage of IENF with any number of swellings. The endpoint “axonal dystrophy” refers to the percentage of IENF with axonal swellings.
- Change from baseline in IENFD in skin punch biopsies at Month 9 and Month 15E;
- Change from baseline in amplitude of wave V on BAEP at a stimulus intensity of 80dB at Months 6, 9, 9E, and 15E;
- Absence of wave V on BAEP at stimulus intensities ranging from 80dB to 40dB at Months 6, 9, 9E, and 15E;
- Incidence of treatmentemergent adverse events (TEAEs);
- Treatment-emergent serious adverse events (TESAEs);
- TEAEs leading to discontinuation;
- Incidence of clinically significant abnormalities in vital signs and ECG;
- Incidence of clinically significant abnormalities in clinical laboratory values.

### 3.3. Secondary Endpoints – Efficacy in TP1+TP2

- Change from baseline in overall and AA SALT score at Month 9 and other time points collected in TP1 and TP2;
- PGI-C score response defined as greatly improved or moderately improved from baseline at Month 9 and other time points collected in TP1 and TP2.

### 3.4. Exploratory Endpoints – Efficacy in TP3

- Change from baseline in overall and AA SALT score at Month 51E and other time points collected in TP3.
- PGI-C score response defined as greatly improved or moderately improved at Month 51E and other time points collected in TP3.

### 3.5. Baseline Variables

Baseline values will be defined as follows for both safety and efficacy endpoints:

- Baseline is defined as the last non-missing measurement obtained before the first dose in the placebo-controlled phase.

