Visit (Months)	1	3	6	9 / EOP	3E	6E	9E	12E	15E	E=Active Therapy Extension Phase Note: Those participants who enter the active therapy extension phase at Month 6 (Visit 5) are to complete at that visit all Month 6 (Visit 5) assessments and then follow the schedule of visits in the active therapy extension phase starting with Month 3E,
Day	31	91	181	271	91E	181E	271E	361E	451E	Day relative to the start of the study phase (ie, Day 1 = start of Placebo-controlled Phase; Day 1E = start of Active Therapy Extension Phase).
Visit Window (±Days)	±3	±7	±7 (See Note)	±7 (See Note)	±7	±7	±7	±7	±7	Note: For the EOP visit only (Month 6 or Month 9/EOP, as appropriate), the window for audiological/BAEP central read (including any repeat assessments if deemed necessary by the central reader) is -7/+21 days. All other assessments, including the primary audiological/BAEP assessments, must be completed within ±7 days.
										Note: Assessment at Month 6 is required only for those eligible participants who enter the active therapy extension phase at Month 6 (See Section 4.1).
Skin punch biopsy for evaluation of axonal dystrophy and IENFD			X (see Note)	X					X	See Section 8.2.8.1 . Note: Assessment at Month 6 is required only for those eligible participants who enter the active therapy extension phase at Month 6 (See Section 4.1). Note: At the EOP visit (Month 6 or Month 9/EOP, as appropriate), the skin biopsy must be collected before the start of Active Therapy Extension Phase.
Tuberculosis testing			X (see Note)	X					X	See Section 8.2.10.1 , Section 8.2.3 , and Section 10.2 . Note: Assessment at Month 6 is required only for those eligible participants who enter the active therapy extension phase at Month 6 (See Section 4.1).
Trial Treatment										

Procedure	Intervention Period									Notes
	TP1: Placebo-controlled Phase			TP2: Active Therapy Extension Phase						
Visit Identifier	3	4	5	6	7	8	9	10	11	Visit 6 (Month 9/EOP), the last visit of the placebo-controlled phase, is also the first visit of the active therapy extension phase.
Visit (Months)	1	3	6	9 / EOP	3E	6E	9E	12E	15E	E=Active Therapy Extension Phase Note: Those participants who enter the active therapy extension phase at Month 6 (Visit 5) are to complete at that visit all Month 6 (Visit 5) assessments and then follow the schedule of visits in the active therapy extension phase starting with Month 3E,

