Visit Window (±Days)	±3	±7	±7 (See Note)	±7 (See Note)	±7	±7	±7	±7	±7	Note: For the EOP visit only (Month 6 or Month 9/EOP, as appropriate), the window for audiological/BAEP central read (including any repeat assessments if deemed necessary by the central reader) is -7/+21 days. All other assessments, including the primary audiological/BAEP assessments, must be completed within ±7 days.
										audiological/BAEP assessments (including the central read confirmation and any repeat assessments if deemed necessary by the central reader) are completed. Active therapy is dispensed (via on-site visit or shipping) only once all the above procedures are completed. Refer to the IRT reference manual for dispensing additional double-blind therapy.
Study intervention administration	X	X	X	X	X	X	X	X		See Section 6.1 .
Study intervention accountability and compliance	X	X	X	X	X	X	X	X	X	See Section 6.2 and Section 6.4 .
Clinical Assessments										

Procedure	Intervention Period									Notes
	TP1: Placebo-controlled Phase				TP2: Active Therapy Extension Phase					
Visit Identifier	3	4	5	6	7	8	9	10	11	Visit 6 (Month 9/EOP), the last visit of the placebo-controlled phase, is also the first visit of the active therapy extension phase.
Visit (Months)	1	3	6	9 / EOP	3E	6E	9E	12E	15E	E=Active Therapy Extension Phase Note: Those participants who enter the active therapy extension phase at Month 6 (Visit 5) are to complete at that visit all Month 6 (Visit 5) assessments and then follow the schedule of visits in the active therapy extension phase starting with Month 3E,
Day	31	91	181	271	91E	181E	271E	361E	451E	Day relative to the start of the study phase (ie, Day 1 = start of Placebo-controlled Phase; Day 1E = start of Active Therapy Extension Phase).
Visit Window (±Days)	±3	±7	±7 (See Note)	±7 (See Note)	±7	±7	±7	±7	±7	Note: For the EOP visit only (Month 6 or Month 9/EOP, as appropriate), the window for audiological/BAEP central read (including any repeat assessments if deemed necessary by the central reader) is -7/+21 days. All other assessments, including the primary audiological/BAEP assessments, must be completed within ±7 days.
SALT		X	X	X	X	X	X	X	X	See Section 8.1.2.1 . At Month 6, any participant with a baseline overall SALT score ≤75 will have the option to enter the active therapy extension phase if the overall SALT score at Month 6 has increased from baseline by ≥25 points.

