BAEPs will be measured at screening and at Months 6, 9, 9E, and 15E, or early termination for all participants. IENF will be assessed at Day 1, Month 9, and Month 15E, or early termination. Participants who enter the active therapy extension phase at Month 6 will have a skin punch biopsy taken at Month 6 for IENF assessments instead of at Month 9. The skin biopsy must be collected before the start of Active Therapy Extension Phase.

Participants who discontinue the study due to a neurological or auditory AE will have assessments performed at the time of discontinuation and repeated at 6 months after the last dose of study intervention (see Section 10.7).

Treatment Period 3 (TP3):

The total duration for TP3 will be of variable length for individual participants; assuming a participant does not require discontinuation per protocol. A participant may continue to receive PF-06651600 in TP3 for a maximum of an additional 36 months or until availability of commercial product in their country, or until the Sponsor terminates the study in that country, whichever occurs first.

In TP3, participants will receive 50 mg QD PF-06651600. The total duration of participation in TP3 is approximately 37 months, including up to 36 months study intervention, and a follow up period of 4 weeks after completion or discontinuation of study intervention (see Section 1.2 Schema).

Observation Period:

If study intervention is permanently discontinued, the participant will be asked to remain in the study after the Follow-up visit without study intervention, and continue to comply with study visit schedules for approximately 2 years after the last dose of study intervention or until study end, whichever occurs first; refer to Section 7.1.1.1 for further details.

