9.4.3. Safety Analyses

The safety analyses will be summarized by initial treatment group in the safety population based on observed data. The baseline is defined as the last measurement before the first dose in the placebo-controlled phase.

All standard safety summary such as the incidence of safety events will be summarized by the initial treatment group for the placebo-control phase, the active therapy extension phase and TP3 extension phase. For initial active group, the overall summary for the whole study duration will also be provided.

PCD CSR (Month 9; TP1)	
Endpoint	Statistical Analysis Methods
Primary	
 The primary endpoint is change from baseline in I-V interwave latency on BAEP at Month 9. It will be analyzed using linear mixed-effects model with baseline, treatment group, visit (Months 6 and 9) and treatment group by visit interaction as fixed effects, and subject as a random effect with unstructured covariance matrix assumption. For participants who switch to the active therapy extension phase at Month 6, only their data through Month 6 will be included in the analysis of the placebo-controlled period. The estimated means, with their standard errors and 95% confidence intervals based on the model will be presented.
Secondary	
 Change from baseline in I-V interwave latency on BAEP during the placebo-controlled phase will be analyzed using linear mixed-effects model with baseline, treatment group, visit (Months 6 and 9) and treatment group by visit interaction as fixed effects, and participant as a random effect with unstructured covariance matrix assumption. The estimated means, with their standard errors and 95% confidence intervals based on the model will be presented. For data in the active therapy extension phase, descriptive statistics will be presented. For change from baseline in IENFD at Month 9 and Month 15E and change from baseline in axonal dystrophy in skin punch biopsies at Month 9 and Month 15E: descriptive statistics will be presented. Change and percent change from baseline in amplitude of wave V: the same method linear mixed-effect model as

PCD CSR (Month 9; TP1)	
Endpoint	Statistical Analysis Methods

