10.9.4. Month 9 Visit Window

The visit window for the special safety assessments at Month 9 in the setting of a public health emergency is expanded to -7 / +60 days. The usual safety assessments are to be completed as above. The full month 9 visit including the special safety assessments (audiological evaluations, neurological evaluation, and the skin biopsy) have until +60 days to be completed onsite or at the designated ancillary center. If required Special Safety Assessments (Section 10.9) cannot be performed at Month 9, the participant will not be allowed into the active therapy extension phase and must follow Early Termination procedures (Section 7.1).

Double-blind investigational product is dispensed until all the specialized safety assessments have been completed. The site staff should contact the IMPALA Help Desk for assistance.

Active therapy investigational product is dispensed only after all the special safety assessments have been completed and is the start of the extension portion of the study.

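### For participants who move from placebo to ritlecitinib, the SAP describes no paired pre-drug to on-drug change in BAEP or biopsy; adding one is a cheap improvement, not the repair of an error

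*SAP*

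**What the plan says.** The two documents agree on baseline. SAP 3.5 states: "Baseline is defined as the last non-missing measurement obtained before the first dose in the placebo-controlled phase". Protocol 9.4.3 states: "The baseline is defined as the last measurement before the first dose in the placebo-controlled phase". Under the schedule of activities this is the screening recording for BAEP and the Day 1 sample for biopsy.

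Protocol 4.1 fixes the BAEP visits: "BAEPs will be measured at screening and at Months 6, 9, 9E, and 15E, or early termination for all participants". Biopsies follow at Month 9 and Month 15E, and participants who switch early "will have a skin punch biopsy taken at Month 6 for IENF assessments instead of at Month 9".

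SAP 6.2.1 to 6.2.4 express I-V latency, axonal swellings, IENFD and wave V amplitude as change from that one baseline, with descriptive summaries in the extension. For supplemental CSR 1, SAP 8.2 gives these by-visit tables one column for the whole placebo-to-ritlecitinib sequence. SAP 3.5, 6.2, 8.2 and 9 define no second baseline and no change from the end of the placebo phase (EOP).

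The protocol nevertheless requires a pre-drug value. On the biopsy, the TP1/TP2 schedule says "the skin biopsy must be collected before the start of Active Therapy Extension Phase". On BAEP, the dispensing note lists the neurological and audiological/BAEP assessments, including the central read and any repeats, and then says "Active therapy is dispensed (via on-site visit or shipping) only once all the above procedures are completed". Under the emergency provisions of Protocol 10.9.4, if the Month 9 special assessments cannot be done, "the participant will not be allowed into the active therapy extension phase".

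**The concern.** The BAEP and biopsy objectives are about participants treated with the drug. In the placebo-to-ritlecitinib arm, Month 9E is the recording after nine months on drug. Protocol 4.2 ties that duration to the dog findings and uses it to justify the length of TP1. Up to about 30 further participants therefore have a recording before drug and another after nine months on it. The planned table shows their result only as a change over about 18 months, half of it on placebo.

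Any shift during the placebo period enters the extension figure one for one. It could make an on-drug change look larger or smaller than it was. Elsewhere the SAP does separate drug time from placebo time: the adverse-event risk periods in SAP 3.6.1 split at the first TP2 dose, and Table 4 shows this arm's TP2 experience on its own for adverse events, laboratory values and vital signs. The BAEP and biopsy change endpoints, which the trial was designed around, have no equivalent.

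**Working it through.** **1. The plan's own precision figure.** Inputs from Protocol 9.2 and the sample-size section of the SAP: SD 0.2 ms (published range 0.1 to 0.3), SD of change taken as similar to SD of the score, 30 per group. Half-width = 1.96 × 0.2 / √30 = 0.072 ms; with t on 29 df it is 0.075 ms. Both round to the stated 0.07 ms.

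**2. What the extension change spans.** Nominal days come from the schedule of activities, counted from Day 1. A Month 9 switcher starts active drug at Day 271, after 270 days on placebo. Days on drug are 270 at Day 271E and 450 at Day 451E.

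| | Month 9E | Month 15E |
|---|---|---|
| Month 9 switchers, placebo share | 270/(270+270) = 50% | 270/(270+450) = 37.5% |
| Month 6 switchers, placebo share | 180/(180+270) = 40% | 180/(180+450) = 28.6% |

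These are shares of time. The documents give no placebo-period drift in ms or in fibre density, so no bias can be calculated from them.

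**3. What the planned tables allow.** For one participant, (Month 9E − baseline) − (Month 9 − baseline) = Month 9E − Month 9. The mean on-drug change can therefore be recovered from two printed means, but only if the same people contribute to both. They need not. Month 6 switchers skip the Month 9 visit (Protocol 4.1) yet can appear at Month 9E, and anyone who leaves between the visits counts only at the first. The SD of the difference cannot be recovered, because it depends on a correlation that is not tabulated.

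**4. Precision of a paired summary.** If the SD of on-drug change is also 0.2 ms (an assumption extending the plan's own):
- paired, n = 30: 1.96 × 0.2 / √30 = 0.072 ms;
- paired, n = 24 (assumed 20% loss): 1.96 × 0.2 / √24 = 0.080 ms;
- subtracting two printed means as if independent, n = 30: 1.96 × 0.2 × √(2/30) = 0.101 ms, which is √2 ≈ 1.4 times wider.

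Equal SDs for score and change imply a between-visit correlation of 0.5. For assumed correlations of 0.3 to 0.9, with score SD 0.2 ms and n = 30, the paired t half-width runs from 0.088 to 0.033 ms.

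**5. What a new baseline cannot remove.** If drift were linear in time, the part falling during drug exposure would stay: 270/540 = 50% of the total at Month 9E and 450/720 = 62.5% at Month 15E.

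**The case against.** The strongest reply is that the placebo period is not hidden. SAP 6.1 reports the placebo arm's Month 9 latency change with its standard error and 95% CI, by ear side. SAP 6.2.4 models wave V amplitude at Months 6 and 9, and SAP 6.2.2 and 6.2.3 describe biopsy change at Month 9/EOP. A reader can see whether the arm moved on placebo. For IENFD, Protocol 4.2 also cites a study in which density in healthy controls did not change significantly across 2 to 3 years, which weakens the worry for that endpoint. Subject listings are planned (SAP 6.7), wave V absence needs no baseline, and the longest exposure is in the arm randomised to ritlecitinib.

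Most of this stands, and it narrows the point to the paired change, its SD and matched participants. The cited study concerns density in healthy controls, so it does not speak to axonal swellings or BAEP. Listings permit derivation by hand but are not a summary.

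A reader might go further and infer that the single baseline is a mistake, or that half of the Month 9E figure is bias. The documents support neither. A common baseline is right for the randomised comparison, and 50% is a share of days. Nor can one say that no such table exists anywhere: the SAP version history refers to separate table specifications that are not available here. The supportable statement is that the SAP describes none.

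**Conclusion.** The point holds as a low-priority improvement. In the placebo-to-ritlecitinib arm, the extension BAEP and biopsy changes combine placebo time and drug time (nominally 270 of 540 days at Month 9E, 270 of 720 at Month 15E). The SAP describes no within-participant summary from the mandated pre-drug measurement. The effect on the reported means is unknown and may be close to zero. The gain is a properly paired estimate in up to about 30 more treated participants. For latency its half-width would be about 0.07 ms, or about 0.08 ms with 24 completers, if the SD of on-drug change is 0.2 ms. The result would be supportive only, because nobody remains on placebo in TP2.

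**What to change.** Keep all common-baseline tables.

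- **SAP 3.5:** for the placebo-to-ritlecitinib arm only, add an active-phase baseline. This is the last non-missing centrally confirmed BAEP, and the last biopsy, taken during TP1 and before the first TP2 dose. Early switchers use their Month 6 values. Screening and Day 1 values are not carried forward.
- **SAP 6.2.1 and 6.2.4:** in supplemental CSR 1, report change from this baseline in I-V latency and wave V amplitude at Months 9E and 15E, by ear side.
- **SAP 6.2.2 and 6.2.3:** do the same for axonal swellings and IENFD at Month 15E.
- **Content:** n, mean and SD, with a 95% CI if wanted. Footnote any Month 9 switcher whose baseline is a Month 6 BAEP, since 90 placebo days then remain in the interval (90/360 = 25% at Month 9E, 90/540 = 17% at Month 15E). The dispensing rule should make this uncommon.
- **Label:** supplementary, uncontrolled, added after the sponsor was unblinded for the PCD analysis (Protocol 6.3.1), and not for comparing arms.

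The cost is one derived variable and a few extra tables. No new data, visits or procedures are needed. There is precedent: SAP version 4.0 records normalised IENFD and percent change in wave V amplitude as additions made to help interpret the secondary endpoints. The limit is that, with no concurrent control, drift during drug exposure remains in the estimate.
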